### Session 4 and 5: Stimulation 1 and 2 (3 hours)

- Motor thresholding using single pulse TMS for use in future sessions will be performed once for each participant on the first day of stimulation, and held constant for the following stimulation session.
- Before practice and performance of the cognitive control task, the TMS coils will be positioned over the targeted region.
- During performance of the task, stimulation will be delivered on every trial.

CONFIDENTIAL

- During stimulation, white noise will be played for the participants to reduce neural effects of auditory entrainment of rhythmic TMS.
- At the end of the session, participants will receive \$40, and \$60 in compensation for sessions 4, and 5, respectively.

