### 11.1 STATISTICAL ANALYSIS STRATEGIES

The statistical analysis plan below aligns with the aims that are described in Section 2.3. all statistical estimates of population parameters will be tabulated along with corresponding confidence intervals (CIs) to convey levels of precision / imprecision. All hypothesis tests that yield large p-values ( $p>0.05$ ) will be reported as being inconclusive.

*Phase One* overarching goal: Investigate the causal role of frontal theta and parietal alpha oscillations in the prioritization and suppression of working memory representations. To control for non-specific effects of rhythmic TMS, we will use an active control: arrhythmic TMS (randomized inter-pulse-interval) that is matched to the target stimulation in number of pulses and temporal duration. All analyses will be performed on the difference from condition-matched arrhythmic TMS. The key analyses are built upon a three-way parallel arms design: with factors TMS frequency (theta versus alpha), location (frontal versus parietal), and cue direction (left versus right retro-cue). There is an equal number of trials for each of these conditions and there are 75 trials for each condition per participant.

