Aim 2 (primary outcome): Stimulation is hypothesized to increase the targeted frequency of stimulation relative to arrhythmic stimulation. This aim will provide evidence of target engagement, i.e. that stimulation is effective at modulating the targeted rhythm. Using Morlet wavelet convolution, the amplitude of theta and alpha oscillations will be estimated during task performance. The average across trials for each conditions will be calculated and baseline corrected using decibels to the time before the encoding array (700 to 300 milliseconds). Then, the average amplitude within the individual theta (ITF  $+$ /- 1 Hz) and alpha frequency (IAF  $+$ /- 1 Hz) band will be calculated for the second half of the train of TMS pulses. Previous research has shown that amplitude increase from stimulation increases over the course of the TMS train. Frontal-theta and parietal-alpha amplitude values will be submitted to a two-way repeated-measures ANOVA with TMS frequency by TMS site. We hypothesize to find a significant interaction ( $p < 0.05$ ) between TMS site and TMS frequency such that theta amplitude in frontal cortex increases greater for TMS to frontal in theta frequency and alpha amplitude in parietal cortex increases greater for TMS to parietal cortex in alpha frequency. Post-hoc t-tests will be performed using Tukey's method to control for multiple comparisons. *Sensitivity analysis*: To understand the specificity of this effect, the time-course for the impact of stimulation of amplitude will be plotted as well as the topographic plot for our effects. Cluster analysis will be used to estimate the spread of our effect in time and space. These analyses provide evidence to the robustness of the

impact of stimulation on amplitude.

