**Aim 5 (secondary outcome):** Stimulation that is aligned to the endogenous activity of the brain is hypothesized to entrain neural activity. Inter-trial phase coherence (ITPC) quantifies alignment of neural oscillations across trials. Stimulation in frontal-theta and parietal-alpha is proposed to increase ITPC in a frequency specific manner relative to control stimulation. A similar method for extracting instantaneous phase is used as that used to extract instantaneous amplitude (Aim 2). ITPC is calculated as the average phase angle in complex space of unit vectors across trials, then taking the magnitude of the resulting vector. These ITPC values are then averaged for the second half of the TMS train as described in (Aim 2). Frontal-theta and parietal-alpha ITPC values will be submitted to a two-way repeated-measures ANOVA with TMS frequency by TMS site. We hypothesize to find a significant interaction ( $p < 0.05$ ) between TMS site and TMS frequency such that theta ITPC in frontal cortex increases greater for TMS to frontal in theta frequency and alpha ITPC in parietal cortex increases greater for TMS to parietal cortex in alpha frequency. Post-hoc t-tests will be performed using Tukey's method to control for multiple comparisons. *Sensitivity analysis:* Similar to the sensitivity analysis of Aim 2, the time-course and topographic plots with cluster analysis will quantify the spread of these effects.

**Phase Two Overarching Goal:** Investigate the causal role of in-phase theta-frequency between frontal and parietal cortex in the prioritization and suppression of working memory representations. To control for non-specific effects of dual-site rhythmic TMS, we will use an active control: arrhythmic TMS (randomized inter-pulse-interval). Two

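### Aims 2, 3 and 5 do not say which EEG signal fills which ANOVA cell; on the natural reading, a response to rhythm that is the same from either coil position produces the predicted interaction

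*Combined protocol and SAP*

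**What the plan says.** Section 11.1 gives the purpose of Aim 2 (primary) as follows: "This aim will provide evidence of target engagement, i.e. that stimulation is effective at modulating the targeted rhythm". The analysis is "Frontal-theta and parietal-alpha amplitude values will be submitted to a two-way repeated-measures ANOVA with TMS frequency by TMS site", and the success criterion is "We hypothesize to find a significant interaction ( $p < 0.05$ ) between TMS site and TMS frequency". The expected pattern is that "theta amplitude in frontal cortex increases greater for TMS to frontal in theta frequency and alpha amplitude in parietal cortex increases greater" when alpha trains go to parietal cortex. Aim 5 (secondary) repeats this for phase coherence: "Frontal-theta and parietal-alpha ITPC values will be submitted to a two-way repeated-measures ANOVA with TMS frequency by TMS site". Aim 3 (secondary) uses the Aim 2 method with the mirror-image signals, frontal alpha and parietal theta.

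Every Phase One value is a control-subtracted value: "All analyses will be performed on the difference from condition-matched arrhythmic TMS". For spatial specificity, Aim 2 adds a time course, a topographic plot and this: "Cluster analysis will be used to estimate the spread of our effect in time and space". These are listed as sensitivity analyses and no decision rule is attached to them.

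The protocol recognises that rhythmic TMS can drive the EEG through hearing. For Sessions 4 and 5, "white noise will be played for the participants to reduce neural effects of auditory entrainment of rhythmic TMS". Section 4.1 notes that theta trains sound slower than alpha trains.

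**The concern.** Target engagement at a site means that a signal rises more when the coil is over that site than when the same train is delivered elsewhere. Testing this needs one signal compared across two coil positions. The plan instead enters two different signals into one frequency-by-site table.

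If frontal sessions supply frontal theta and parietal sessions supply parietal alpha, the site factor changes the measured signal together with the coil position. Frontal theta during parietal TMS, and parietal alpha during frontal TMS, then drop out. A brain-wide response to the rhythm would appear as the hypothesised crossover and be reported as engagement of the target. A primary conclusion is at stake, and so is the entrainment conclusion of Aim 5.

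**Working it through.** **1. The plan's own figures (Section 11.2).** A two-sided paired t-test at 0.05 with a noncentral t gives N = 48 for effect size 0.532 (power 95.05%), N = 21 for 0.83 (95.11%) and N = 44 for 0.56 (95.26%). All three reproduce. The 0.83 and 0.56 figures are for rhythmic versus arrhythmic TMS. Section 11.2 gives no power or error rate for the Aim 2 or Aim 5 interaction.

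**2. Cell means under purely non-local following.** Let theta trains raise theta by gT and alpha trains raise alpha by gA, equally from either coil position, with no local effect. Subtracting arrhythmic TMS leaves these intact, because randomised intervals offer no steady rhythm to follow. The interaction is L = (frontal site, theta TMS) − (frontal, alpha) − (parietal, theta) + (parietal, alpha).

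| How cells are filled | F-theta | F-alpha | P-theta | P-alpha | L |
|---|---|---|---|---|---|
| Signal of the stimulated site | gT | 0 | 0 | gA | gT + gA |
| Separate ANOVA, frontal theta | gT | 0 | gT | 0 | 0 |
| Separate ANOVA, parietal alpha | 0 | gA | 0 | gA | 0 |
| Signal of the stimulated frequency | gT | gA | gT | gA | 0 |
| Average of the two signals | gT/2 | gA/2 | gT/2 | gA/2 | 0 |

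For Aim 3 the site-tied cells are 0, gA, gT, 0, so L = −(gT + gA). That is the hypothesised direction without any theta-alpha antagonism.

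**3. Rejection rates for the site-tied filling.** Assumptions: SD 1 for each rhythmic-minus-arrhythmic value, independent cells, two-sided 0.05.
- 48 participants with both sites: SD(L) = √4 = 2, so dz = (gT + gA)/2, with 47 df.
- 24 + 24 in parallel (assumed split): each participant's frequency difference has SD √2, so the noncentrality is (gT + gA)/(√2 × √(2/24)), with 46 df.

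| gT, gA | L | dz (48) | Significant, 48 within | Noncentrality (24 + 24) | Significant, 24 + 24 |
|---|---|---|---|---|---|
| 0.2, 0.2 | 0.40 | 0.20 | 27% | 0.98 | 16% |
| 0.5, 0.5 | 1.00 | 0.50 | 92% | 2.45 | 67% |
| 0.56, 0.83 | 1.39 | 0.695 | 99.7% | 3.40 | 91.5% |

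With a between-cell correlation of 0.5, the first row becomes 48% and 27%, and the last row 100% and 99.7%. Simulations of 20,000 trials at zero correlation agree for the first and last rows (27.1% and 16.0%; 99.7% and 91.4%). The separate-signal and frequency-tied fillings simulate at about 5%.

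**4. Do the planned follow-ups catch it?** With site-tied cells, the Tukey comparison of frontal-theta TMS with parietal-theta TMS sets frontal theta against parietal alpha (gT against 0), so it does not test locality. The topographic and cluster displays could reveal a widespread response, but nothing makes the engagement conclusion depend on them.

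**5. Power of a same-signal, same-frequency contrast between coil sites, if the effect is truly local.** Same assumptions. With 48 within, dz = g/√2: 0.56/√2 = 0.396 gives 77%, and 0.83/√2 = 0.587 gives 98%. With 24 + 24, the noncentrality is g√12: 1.94 gives 48%, and 2.88 gives 80%.

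**The case against.** The strongest reply is that the plan never says the cells are tied to the stimulated site. A reader might infer that the Aim 2 test is definitely invalid. The documents do not support that: the filling is undefined, and the hypothesis wording also fits comparing each signal across coil sites. Separate ANOVAs, frequency-tied cells and averaged cells all hold 5% under non-local following. This part of the reply stands. Against it, the text describes a single ANOVA with a single predicted interaction, Aim 3 also refers to one ANOVA, and its exploratory antagonism metric is taken within the site of interest. The site-tied reading is therefore natural and is not excluded.

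A second reply is that the following may be small. White noise is planned, delivered through sealed ear-buds (Section 8.2.1, Physical), and the documents give no residual size. This also stands: the 0.5 and 0.56/0.83 rows are scenarios, not estimates. At 0.2 SD the rate is still three to five times nominal (16% to 27% with independent cells).

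A reader might also infer that the causal reading of Aim 1 collapses with Aim 2. It does not. Aim 1 uses one outcome, capacity k, in all four cells, so an effect of rhythm that is the same from either coil position cancels in its interaction.

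**Conclusion.** The concern holds in a limited form. The input to a primary ANOVA is unspecified, and a natural way of running it cannot separate local engagement from a coil-independent response to rhythm. Depending on how the cells are filled, the same non-local truth is called significant in 5% of trials or in as many as 99.7%, and the plan leaves that choice open. Aims 3 and 5 are affected in the same way.

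The algebra (L = gT + gA against L = 0) needs no variance assumption beyond equal following at both coil positions and no spill of theta trains into the alpha band. Spill of size h would reduce the site-tied L to gT + gA − h. The percentages rest on unit SD, the stated correlations, the chosen sizes of following, and either 48 participants with both sites or an assumed 24 + 24 split. The split matters because Section 1.5 (version 7.0) and the Section 11.1 introduction describe parallel arms, while Aim 1 in Section 11.1 calls site a within-participant factor. The conclusion is the same either way; only the size changes.

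**What to change.** - State exactly which signal, at which region, enters each cell for Aims 2, 3 and 5.
- Analyse each signal in its own TMS frequency by TMS site model. Require a contrast of the same signal at the same TMS frequency between the two coil sites, each value minus its matched arrhythmic control. For Aims 2 and 5 these are frontal theta under frontal-theta versus parietal-theta TMS, and parietal alpha under parietal-alpha versus frontal-alpha TMS. For Aim 3 the analogous contrasts are frontal alpha under frontal-theta versus parietal-theta TMS, and parietal theta under parietal-alpha versus frontal-alpha TMS.
- Claim a site-specific effect for a signal only if its own contrast is significant. Otherwise report a response that is frequency-specific but not site-specific.
- Do not sum the two signals into one locality contrast. If only parietal alpha were local at 0.83, the sum would have dz = 0.83/2 = 0.415 and would pass about 80% of the time with 48 within, crediting frontal theta with engagement it does not have.
- Reconcile Section 1.5, the Section 11.1 introduction and Aim 1 on whether site varies within or between participants, and run the contrast to match the actual allocation.

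The cost is SAP wording and further values extracted from the Session 4 and 5 EEG; no new data are needed. The claim becomes stricter and power per signal falls to about 77% (theta) and 98% (alpha) with 48 within, or 48% and 80% with 24 + 24. The statement of sufficient power in Section 11.2 should therefore not be extended to these contrasts.

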Aim 4 (secondary outcome): Theta oscillations in frontal cortex are hypothesized to play a causal role in precision of working memory representations. During the probe, the participant responds with a specific color from a comprehensive color wheel. Plus or minus 15 degrees around the color wheel is considered "correct." For the correct trials, the precision is calculated as the distance in degrees from the response of the participant to the actual color of the memory item. To investigate if theta oscillations play a causal role in precision, the impact of theta stimulation on precision relative to arrhythmic and as a function of visual field will be investigated.

Aim 5 (secondary outcome): Stimulation that is aligned to the endogenous activity of the brain is hypothesized to entrain neural activity. Inter-trial phase coherence (ITPC) quantifies alignment of neural oscillations across trials. Stimulation in frontal-theta and parietal-alpha is proposed to increase ITPC in a frequency specific manner relative to control stimulation.

*Phase Two Overarching Goal:* Investigate the causal role of in-phase theta-frequency between frontal and parietal cortex in the prioritization and suppression of working memory representations.

Aim 6 (primary outcome): Stimulation that is delivered in-phase to frontal and parietal cortex in the theta frequency is hypothesized to increased working memory capacity relative to anti-phase theta stimulation. Working memory capacity is quantified using Pashler's metric.

Aim 7 (primary outcome): Stimulation that is delivered in-phase to frontal and parietal cortex in theta frequency is hypothesized to increase functional connectivity between the regions in a frequency specific manner. Functional connectivity will be measured using weighted phase lag index. In addition, we hypothesize that in-phase theta frequency stimulation will increase WPLI magnitude for retro-cues to the right visual field greater than the increase for stimulation with a retro-cue to the left visual field. This hypothesis is motivated by the finding that the left hemisphere processes information for the contralateral visual hemifield and that theta oscillations are linked to the active processing of information.

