#### 4 BASIC STUDY DESIGN

This study is a pilot, five-session study with transcranial magnetic stimulation (TMS), electroencephalography (EEG), and magnetic resonance imaging (MRI) to understand the neural oscillatory basis of output-gating. The first session of the experiment will be screening session, in which participants provide written consent to participate, screened for colorblindness, complete questionnaires, and perform a working memory task with retrospective cues. Participants will be invited back to the second session if they show a benefit to their working memory percent correct by use of the informative retro-cue relative to the uninformative neutral cue. This session will also be used to select the number of items that will be used in the working memory task for subsequent sessions. The criteria for difficulty titration is task performance between 60% and 85% correct for retro-cue trials and a benefit of at least 5% greater than neutral cue trials. Thus, different participants will perform the task with different numbers of items to be encoded into working memory. Titration of task difficulty as described here is critical for experiments that use causal manipulation (e.g. transcranial magnetic stimulation) to modulate performance. If participants are performing at ceiling (close to 100%) or at floor (close to random chance), then any experimental manipulation of behavior is less likely to impact performance as the task is too "easy" or too "hard." For the second session of the experiment,

[figure not shown]

Fig1. Experimental design consists of five sessions. The two phases of the experiment randomize and counterbalanced different parameters of stimulation for the 4th and 5th session. w/ = with. WM = working memory.

participants perform the working memory retro-cue task while EEG is recorded. In addition, participants will complete a simple perception color task in which participants see a color and choose the matching color from the color circle. This task tests for the precision of perception throughout the color circle. The EEG data from the second session will be preprocessed and a Morlet wavelet convolution analysis will be conducted. The resulting spectrogram will be contrasted between the informative retro-cue and uninformative neutral cue to derive the theta frequency with peak amplitude in

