#### 4.1 TREATMENT ASSIGNMENT PROCEDURES

Phase one: Participants will receive stimulation to either the frontal or parietal cortex in a randomized and counter-balanced sequence for the fourth and fifth session. Randomization and counterbalancing is performed by a script that generates a spreadsheet to stimulation ID mapping. Participants are randomized upon entering the fourth session of the experiment. Thus, there is no influence of the experiment on which sequence the participant will receive. Stimulation types are randomized and counter-balanced by a script at the time of the session and defined as theta, alpha, arrhythmic-theta, and arrhythmic-alpha. It should be noted that all analyses are controlled by a within-session contrast that accounts for general sequence effects.

Phase two: Participants are randomized to receive stimulation to both the frontal and parietal cortex in either theta or alpha frequency for both of the fourth and fifth session. A similar randomization procedure will be used as in phase one. Stimulation types are randomized and counter-balanced within a session by a script: in-synchrony, anti-synchrony, arrhythmic-synchrony, and arrhythmic-independent. It should be noted that all analyses are controlled by a within-session contrast by comparing to arrhythmic stimulation.

The primary analysis of the experiment is controlled within-session as a contrast with the arrhythmic control conditions. The difference in site of stimulation for phase one and the auditory difference between theta and alpha stimulation (theta is audibly slower than alpha) precludes double-blinding as the researcher will be aware of this difference in running the experiment. In other words, the study cannot be blinded and there is no attempt to blind the study. Furthermore, the control for each stimulation condition is self-contained within each session. The stimulation sessions for each phase consists of four stimulation conditions (described above) and two task conditions (retro-cue to the left visual field and retro-cue to the right visual field), thus there are a total of 8 conditions total for phase 1 and 4 conditions total for phase 2. With 600 trials per session, then will be 75 trials of each condition for phase 1 and 150 trials of each conditions for phase 2. The order of these trials is randomized for each session for each participant via a script.

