**Aim 4 (secondary outcome):** Theta oscillations in frontal cortex are hypothesized to play a causal role in precision of working memory representations. During the probe, the participant responds with a specific color from a comprehensive color wheel. Plus or minus 15 degrees around the color wheel is considered "correct." For the correct trials, the precision is calculated as the distance in degrees from the response of the participant to the actual color of the memory item. To investigate if theta oscillations play a causal role in precision, the impact of theta stimulation on precision relative to arrhythmic and as a function of visual field will be investigated using a two-way repeated-measures ANOVA: TMS frequency (theta or alpha) and visual field (left and right) for stimulation to frontal cortex. We hypothesize to find an interaction between TMS frequency and visual field such that precision is increased when theta stimulation is applied to the frontal cortex with a retro-cue to the contralateral visual field (right visual field). Post-hoc t-tests will be performed using Tukey's method to control for multiple comparisons. *Sensitivity analysis:* To better understand the impact of stimulation on precision, we will include additional covariates such as the location in the color space and the accuracy for the participant across color space. It is possible that participants will have differences in sensitivity to color changes dependent on the color, so this control analyses accounts for those differences.

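### Aim 4 computes precision only from responses within 15 degrees, which can hide much of a real change, and its metric is an error although the hypothesis is worded as an increase

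*Combined protocol and SAP*

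**What the plan says.** Section 2.3 sets the window: "Plus or minus 15 degrees around the color wheel is considered" correct. Section 11.1, Aim 4 repeats it and defines the outcome: "For the correct trials, the precision is calculated as the distance in degrees from the response of the participant to the actual color" of the remembered item. How the trial values are combined for each participant is not written; a mean is presumably meant.

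The test is a repeated-measures ANOVA with factors "TMS frequency (theta or alpha) and visual field (left and right) for stimulation to frontal cortex". The prediction is an interaction "such that precision is increased when theta stimulation is applied to the frontal cortex" with a retro-cue to the right visual field. The Aim 4 sensitivity analysis reads: "we will include additional covariates such as the location in the color space and the accuracy for the participant across color space". It does not lift the 15-degree restriction.

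Two other provisions fix the setting. Section 4 titrates difficulty to "task performance between 60% and 85% correct for retro-cue trials". Section 4.1 gives the trial count: "With 600 trials per session, then will be 75 trials of each condition for phase 1". Section 11.2 bases the sample size on working memory capacity and oscillatory power; it gives no effect size or power for precision.

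**The concern.** If stimulation sharpens memory, some responses that would have landed outside 15 degrees now land inside. The Aim 4 metric does not count that movement as a gain. The newly included responses tend to lie near the edge of the window, so they offset part of the improvement among the responses already inside. The sets of trials being compared also differ between conditions, because inclusion depends on the response made after stimulation.

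Aim 4 is the plan's only test of whether frontal theta affects precision, and Section 11.1 reports any p-value above 0.05 as inconclusive. A metric that responds weakly to true precision makes that outcome more likely than the recorded data require.

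The direction is a separate matter. A distance from the true colour is an error, so a larger value is worse. The plan calls this quantity precision and predicts an increase, with no inversion or sign rule.

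**Working it through.** **Plan's own figures.** A two-sided paired t-test at alpha 0.05 and 95% power (noncentral t) reproduces Section 11.2: effect size 0.532 gives 48 participants, 0.83 gives 21, and 0.56 gives 44. None of these concerns precision. For trials, 600 / 8 = 75 per condition. At 60% to 85% correct, 75 × 0.60 = 45 to 75 × 0.85 ≈ 64 trials enter Aim 4.

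**Assumptions, not in the documents.**
- Error is Normal(0, σ) with probability 1 − g, and uniform over ±180 degrees (a guess) with probability g. I take g from 0 to 20%.
- The titration figure for percent correct uses the same 15-degree window and still applies in the stimulation sessions.
- The per-participant summary is the mean.

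**Formulas.**
- Density of absolute error: f(x) = 2(1 − g)φ(x/σ)/σ + g/180.
- Share in window: A = (1 − g)[2Φ(15/σ) − 1] + g × 15/180.
- Windowed mean: m = ∫₀¹⁵ x f(x) dx / A. For a flat distribution this is 15/2 = 7.5.
- Windowed metric, two cells: z = [m(σ) − m(0.9σ)] / [√2 × s_w / √(75A)], where s_w is the SD of absolute error inside the window.
- Mixture SD from all 75 trials: z = 0.1σ / [√2 × SE(σ)], with SE from the Fisher information for (σ, g). At g = 0, SE = σ/√150.

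**Worked case, σ = 12, g = 10%.** A = 0.9 × 0.789 + 0.1 × 0.083 = 0.718, so 53.9 trials are kept. The windowed mean falls from 6.592 to 6.397 degrees, a change of 3.0%. With s_w = 4.164, z = 0.195 / (1.414 × 0.567) = 0.243. For the mixture SD, SE = 1.160 and z = 1.2 / (1.414 × 1.160) = 0.731. The ratio is 3.0.

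**Across the band**, with σ solved to match each accuracy and then cut by 10%:

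| Correct | Guesses | σ (deg) | Windowed mean (deg) | Fall in windowed mean | z, windowed | z, mixture SD | Ratio |
|---|---|---|---|---|---|---|---|
| 60% | 0 | 17.8 | 7.07 | 1.4% | 0.109 | 0.866 | 8.0 |
| 60% | 10% | 15.8 | 6.96 | 1.7% | 0.135 | 0.714 | 5.3 |
| 72.5% | 0 | 13.7 | 6.79 | 2.3% | 0.194 | 0.866 | 4.5 |
| 72.5% | 10% | 11.8 | 6.56 | 3.1% | 0.251 | 0.732 | 2.9 |
| 85% | 0 | 10.4 | 6.31 | 3.9% | 0.338 | 0.866 | 2.6 |
| 85% | 10% | 8.1 | 5.69 | 5.8% | 0.483 | 0.751 | 1.6 |
| 85% | 15% | 6.2 | 4.77 | 8.1% | 0.634 | 0.724 | 1.1 |

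The fall divided by 10% is the share of the change that the metric shows: 14% in the first row, 31% in the fourth and 81% in the last. In the fourth row the same change lifts accuracy from 72.5% to 76.6%, so much of the signal goes into the window count that Aim 4 conditions on.

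**Finite-sample check.** I simulated 75-trial maximum-likelihood fits, 1,500 per setting, for five of these rows. The fitted SD was nearly unbiased (for example 11.76 against a true 11.80). The ratios ran from 1.1 (85%, 15% guesses) to 7.1 (60%, no guesses), close to the table.

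The z values carry trial noise only, for two cells of one participant. The ratio does not depend on how many cells enter the contrast, provided trial noise is similar across them.

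**The case against.** The strongest reply is that every size above rests on an assumed error distribution. This stands. The loss shrinks toward the top of the titration band: at 85% correct the windowed mean shows 58% of a 10% change with 10% guesses and 81% with 15%, and the mixture's advantage drops to 1.6 and 1.1. A reader might infer that the window hides most of any real change. The documents do not support that as a general statement.

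The window also has a purpose. It keeps guesses out of the precision measure, and accuracy is analysed elsewhere, through capacity in Aim 1 with overall accuracy as an exploratory addition. That is a partial complement only, because the Aim 1 model has site and frequency as factors and not the visual field that Aim 4 tests. Dropping the window and averaging raw error over all trials would not help: with 10% guesses and 85% correct, a 20% cut in SD gives a signal-to-noise of 0.24 for the raw mean against 1.13 for the windowed one.

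The mixture is a model choice too, and its advantage is computed with that model as the truth. Where several items are held, some responses may report a non-target item, which the simple form ignores. This stands and is carried into the fix.

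On direction, a reader might infer that the plan would count worse recall as support. That is strained: the ordinary meaning of "precision is increased when theta stimulation is applied to the frontal cortex" is that responses lie closer to the true colour. The interaction p-value is the same under either sign.

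**Conclusion.** The concern holds in a bounded form. Selecting on a response that stimulation can change, at 15 degrees, can hide much of a real change in precision, and at low to mid accuracy usually most of it. Under normal error plus uniform guesses within the 60% to 85% band, a 10% cut in error SD moves the windowed mean by about 1.4% to 8%. The all-trial mixture SD is about 1.1 to 5 times as sensitive per participant with 10% to 15% guesses, and up to about 8 times with none.

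A reader might go further and infer that a true theta effect would most likely be reported as inconclusive. That cannot be shown: Aim 4 is a group-level interaction of differences from arrhythmic stimulation, and the documents give neither an effect size nor a between-participant variance for precision.

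The reversed label and the unwritten per-participant summary are faults of definition and need no assumption to see. Aim 4 is a secondary outcome and the primary aims are untouched, so this is a cheap improvement.

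**What to change.** In Sections 2.3 and 11.1, Aim 4:

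- Name the variable response error, state that lower values mean higher precision, give the predicted sign of the interaction, and write down the per-participant summary.
- Estimate precision from all responses in each condition with a von Mises plus uniform mixture. Analyse the SD or concentration, and report the guess rate separately. Consider a non-target-report component where several items are held, and partial pooling across participants if individual fits are noisy.
- Report the share of responses within 15 degrees by the same TMS frequency and visual field factors.
- Keep the 15-degree metric as a sensitivity analysis.

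The cost is SAP wording and a standard model fit to responses already recorded. The downsides are some fitting noise at 75 trials per condition and reliance on a model form, which the retained windowed analysis helps to check.
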